Period	The subdivisions of the trial design (e.g. Screening, Treatment, Follow-up) which are described in the Protocol. Periods define the study phases and will be used in clinical trial database setup and eventually in analysis
Personal data	Participant information collected by the Investigator that is coded and transferred to Novartis for the purpose of the clinical trial. This data includes participant identifier information, study information and biological samples.
Premature participant withdrawal	Point/time when the participant exits from the study prior to the planned completion of all study drug administration and/or assessments; at this time all study drug administration is discontinued and no further assessments are planned
Randomisation number	A unique identifier assigned to each randomised participant
Screen Failure	A participant who did not meet one or more criteria that were required for participation in the study
Source Data/Document	Source data refers to the initial record, document, or primary location from where data comes. The data source can be a database, a dataset, a spreadsheet or even hard-coded data, such as paper or eSource
Start of the clinical trial	The start of the clinical trial is defined as the signature of the informed consent by the first participant
Study treatment	The study treatment, KJX839/Inclisiran for Injection (sub-cutaneous use), is a sterile formulation of inclisiran sodium in water for injection packaged in vial or glass pre-filled syringe (PFS) presentations
Study treatment discontinuation	When the participant permanently stops taking any of the study drug(s) prior to the defined study treatment completion date (if any) for any reason; may or may not also be the point/time of study discontinuation
Treatment arm/group	A treatment arm/group defines the dose and regimen or the combination, and may consist of 1 or more cohorts.
Treatment of interest	The treatment of interest and, as appropriate, the alternative treatment to which comparison will be made. These might be individual interventions, combinations of interventions administered concurrently, e.g. as add-on to standard of care, or might consist of an overall regimen involving a complex sequence of interventions. This is the treatment of interest used in describing the related clinical question of interest, which might or might not be the same as the study treatment.

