6.1 Study treatment

The study treatment, Inclisiran for Injection (SC use), is a sterile formulation of inclisiran sodium in water for injection packaged in vial or glass pre-filled syringe (PFS) presentations. The covid-19 vaccination should not be given within 7 days of receiving IMP.

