6.5.2 Instruction for prescribing and taking study treatment

Study drug injections will be performed by qualified clinical staff delegated by the investigator.

The site of injection is the abdomen; alternative injection sites include the upper arm or thigh. Injections should not be given into areas of active skin disease or injury such as sunburns, skin rashes, inflammation, tattoos or skin infections.

Participants will be administered one s.c. injection of study drug at pre-defined visits as specified in the Assessment Schedule (Section 8) and summarised below.

Participants randomised to group 2 or 3 will receive one injection of inclisiran on Day 1 and a second injection of inclisiran on Day 90.

Injections will be administered after all other study assessments have been completed for the visit.

Should a participant develop signs or symptoms of anaphylaxis when study drug is injected, the investigator or delegate will need to collect a blood sample for tryptase within 30 minutes of the onset of anaphylaxis (or as soon as possible).

All kits of study treatment assigned by the IRT will be recorded in the IRT system.

7 Informed consent procedures

Eligible participants may only be included in the study after providing (witnessed, where required by law or regulation) IRB/IEC-approved informed consent.

Informed consent must be obtained before conducting any study-specific procedures (e.g. all of the procedures described in the protocol). The process of obtaining informed consent must be documented in the participant source documents.

Novartis will provide to investigators in a separate document a proposed informed consent form that complies with the ICH GCP guidelines and regulatory requirements and is considered appropriate for this study. Any changes to the proposed consent form suggested by the investigator must be agreed by Novartis before submission to the IRB/IEC.

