12.1 Analysis sets

The Full Analysis Set (FAS) comprises of all randomised participants with the exception of those mis-randomised participants who did not receive study drug. Mis-randomised participants are defined as not qualified for randomisation and are inadvertently randomised into the study. According to the intent to treat principle, participants will be analysed according to the treatment they have been assigned to during the randomisation procedure. The FAS will be used in analyses for the primary, secondary, **and the efficacy** objectives.

The Safety Set includes all participants who received at least one dose of study treatment. Participants will be analysed according to the study treatment received. This will be the primary population for the safety analyses.

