12.5.2 Safety endpoints

For all safety analyses, the safety set will be used. All tables will be presented by treatment group.

Safety summaries (tables, figures) include only treatment emergent events (events started after the first dose of study medication or events present prior to start of double-blind treatment but increased in severity based on preferred term) with the exception of baseline data which will also be summarised where appropriate (e.g. change from baseline summaries). In addition, a separate summary for deaths including on treatment and post treatment deaths will be provided.

In particular, summary tables for adverse events (AEs) will summarise only treatment emergent AEs.

Adverse events

The number (and percentage) of participants with serious adverse events and treatment emergent adverse events leading to discontinuation (started after the first dose of study medication) will be summarised in the following ways:

- by treatment, primary system organ class and preferred term.
- by treatment, primary system organ class, preferred term and maximum severity.
- by treatment, Standardised MedDRA Query (SMQ) and preferred term.

Separate summaries will be provided for study medication related adverse events, death, serious adverse events, other significant adverse events leading to discontinuation.

A participant with multiple adverse events within a primary system organ class is only counted once towards the total of the primary system organ class.

Adverse events which will be counted for a specific treatment period are those which are treatment-emergent. These events are those with an onset after the start of the treatment period, or which were present prior to the start of the treatment period but increased in severity, changed from being not suspected to being suspected of study drug relationship, or developed into SAEs after the start of the treatment period.

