#### 2.2 Analysis sets

Screened Set (SCR) will include all participants who provided study informed consent.

**Randomized set (RAN)** will consist of all participants who received a randomization number, regardless of whether study treatment received or not.

| Novartis | Confidential | Page 13 of 37           |
|----------|--------------|-------------------------|
| SAP      |              | Study No. CKJX839A1GB01 |

**Full Analysis Set (FAS)** will consist of all randomised participants with the exception of those mis-randomised participants who did not receive study drug. Mis-randomised participants are defined as not qualified for randomisation and are inadvertently randomised into the study. According to the intent to treat principle, participants will be analysed according to the treatment they have been assigned to during the randomisation procedure. The FAS will be used in analyses for the primary, secondary, **and the study** efficacy objectives.

**Safety Set (SAF)** will consist of all participants who received at least one dose of study treatment. Participants will be analysed according to the study treatment received. This will be the primary population for the safety analyses.

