## 2.7 Safety analyses

For all safety analyses, the safety set will be used.

Safety summaries (tables, figures) will include only treatment emergent adverse events (i.e. adverse events started after the first dose of study treatment or adverse events that were present prior to start of study treatment but increased in severity during the course of the study). Listings will include all data.

Vital signs values that have complete data and time values will be allocated to pre- or post-dose assessment (as per protocol) based on the actual date/time. For values with missing date/time, scheduled visit date and time will be used. This rule will be applied to data from scheduled visits only. If a measurement scheduled as pre-dose is actually performed post-dose, or vice versa, the data will not be used for by visit/time point summary.

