#### 2.7.1 Adverse events (AEs)

The number (and percentage) of participants with TEAEs will be summarized by treatment groups and overall in the following ways:

- By treatment, primary system organ class (SOC) and preferred term (PT).
- By treatment, primary system organ class (SOC), PT and maximum severity.
- By treatment, Standardized MeDRA query (SMQ) and PT.

Separate summaries will be provided for study medication related adverse events, death, serious adverse events, other significant adverse events leading to treatment discontinuation.

Unless otherwise specified, SOCs will be sorted alphabetically and, within each SOC, the PTs will be sorted in descending order of frequency in the total column. A participant with multiple

| Novartis | Confidential | Page 23 of 37           |
|----------|--------------|-------------------------|
| SAP      |              | Study No. CKJX839A1GB01 |

adverse events within the same PT, the AE will be counted only once. A participant with multiple adverse events within a primary system organ class is only counted once towards the total of the primary system organ class. In case of summary by severity or relationship to study drug, summary will be done using the most severe or related occurrence respectively. Listing of all AEs and SAEs will be provided.

**AE reporting for CT.gov and EudraCT**: For the legal requirements of clinicaltrials.gov and EudraCT, two required tables on treatment emergent adverse events which are not serious adverse events, on treatment emergent serious adverse events and SAE suspected to be related to study treatment will be provided by system organ class and preferred term on the safety set population.

If for a same patient, several consecutive AEs (irrespective of study treatment causality, seriousness and severity) occurred with the same SOC and PT:

- a single occurrence will be counted if there is ≤ 1 day gap between the end date of the preceding AE and the start date of the consecutive AE
- more than one occurrence will be counted if there is > 1 day gap between the end date of the preceding AE and the start date of the consecutive AE

For occurrence, the presence of at least one SAE / SAE suspected to be related to study treatment / non SAE has to be checked in a block e.g., among AE's in a  $\leq 1$  day gap block, if at least one SAE is occurring, then one occurrence is calculated for that SAE.

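### As written, the Safety Set excludes the whole control arm, so the planned safety summaries have no control column

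*SAP*

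**What the plan says.** **Membership.** SAP 2.2 states that the Safety Set "will consist of all participants who received at least one dose of study treatment". Protocol 12.1 agrees: "The Safety Set includes all participants who received at least one dose of study treatment". Both group participants by the treatment they actually received.

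**What study treatment means.** The protocol glossary reads "The study treatment, KJX839/Inclisiran for Injection (sub-cutaneous use), is a sterile formulation of inclisiran sodium in water for injection", and Protocol 6.1 reads "The study treatment, Inclisiran for Injection (SC use), is a sterile formulation of inclisiran sodium in water for injection". The SAP gives no definition of its own.

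**Who receives it.** Protocol 6.5.2: "Participants randomised to group 2 or 3 will receive one injection of inclisiran on Day 1", with a second injection at Day 90. Group 1 has background lipid-lowering therapy plus behavioural support.

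**Where the set is used.** SAP 2.7 applies it to every safety analysis. SAP 2.7.1 says the ClinicalTrials.gov and EudraCT tables "will be provided by system organ class and preferred term on the safety set population". SAP 2.4 makes it the default for the treatment and medication summaries.

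**Which events count.** Protocol 12.5.2 says the safety summaries "include only treatment emergent events (events started after the first dose of study medication", or prior events that worsened. SAP 2.7 likewise counts "adverse events started after the first dose of study treatment". A later paragraph of Protocol 12.5.2 instead counts events that begin once the treatment period has started.

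**What is collected.** Under Protocol 9.2 and 10.3.3, SAEs are monitored and reported in all randomised participants, from consent until 30 days after the end-of-study visit.

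**The concern.** Protocol 3.2 and SAP 1.2 list the SAE profile among the assessments for a secondary objective framed as inclisiran, with or without support, against standard of care plus support. A safety population that requires an inclisiran injection cannot supply the second half of that comparison. The trial would hold the control-arm SAEs and deaths but would not tabulate them. The trial is open-label, and the tables posted on public registries would show the inclisiran arms alone.

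Adding Group 1 to the set would not be enough. Unless a start date is written down for participants who are never injected, a programmer would have to choose one after the data exist.

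The medication summaries matter too. New or changed lipid-lowering therapy in the control arm bears on how the LDL-C result is read, and its planned summary by arm is run on the Safety Set.

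**Working it through.** **1. Planned numbers.** Nine hundred participants are allocated 1:1:1, so 300 per arm. The stated sample size reproduces: for d = 0.3, one-sided 0.025 and 90% power, n = 2(1.960 + 1.282)²/0.3² ≈ 234 evaluable per arm, and 234/(1 − 0.20) ≈ 293, rounded up to 300 in the plan. That figure is not in question.

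**2. Apply the membership rule.** Assume that everyone in Groups 2 and 3 is injected and that nobody in Group 1 is injected by mistake.

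| Arm | Randomised | Safety Set as written |
|---|---|---|
| Group 1 | 300 | 0 |
| Group 2 | 300 | 300 |
| Group 3 | 300 | 300 |

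Omitted: 300/900 = 33.3% of randomised participants and 300/300 = 100% of controls. A Group 1 participant injected in error would enter the set but, grouped by treatment received, would not form a control column.

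**3. Look for another safety population.** SAP 2.2 calls the Safety Set the primary population for safety, which might hint at a second one. None is named, and SAP 2.7 applies this set to all safety analyses.

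**4. Look for a start date for undosed participants.**

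- SAP 2.1.1 falls back to the randomisation visit for study day, baseline, post-baseline and the Day 1 of the visit windows. SAP 2.3.1 does the same for duration on study.
- SAP 2.7 (treatment emergence) has no fallback.
- SAP 5.1.2 (AE start dates) compares with the study drug start date, and SAP 5.1.3 (medication start dates) with the treatment start date. Neither has a fallback.
- Protocol 12.5.2 uses both first dose and start of the treatment period. The second can work without a dose, because Table 8-1 schedules Day 1 for Group 1, by phone if preferred.

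**5. Check what the randomisation visit is.** Protocol 6.2.2 and 8.2 place randomisation at screening/baseline, within 14 days before treatment. Protocol 12.3, SAP 2.4.2 and item TRT03 in SAP Table 5-4 equate it with Day 1. Copying the fallback alone could therefore give Group 1 an earlier start than the injected arms.

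**6. Illustrate the stakes.** The documents give no SAE incidence, so the values below are assumptions, taken as equal in the arms. The 95% half-width for a risk difference is 1.96√[p(1 − p)(1/n₁ + 1/n₂)].

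| Assumed SAE incidence | Control participants with an SAE left out (300p) | Half-width, 300 v 300 | Half-width, 600 v 300 |
|---|---|---|---|
| 2% | 6 | 2.2 points | 1.9 points |
| 5% | 15 | 3.5 points | 3.0 points |
| 10% | 30 | 4.8 points | 4.2 points |
| 15% | 45 | 5.7 points | 4.9 points |

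A descriptive comparison of this precision is available from data the trial already collects; the plan as written does not produce it.

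**The case against.** The best reply is that a control column was plainly meant. Protocol 12.5.2 asks for all safety tables by treatment group. SAP 2.4.1 defines exposure to lipid-lowering therapy, with first and last doses, in a section run on the Safety Set. Protocol 6.4.1 uses the term study medication for standard of care as well. If background therapy counts as study treatment, most of Group 1 enters the set.

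As evidence of intent, this stands; as a rule, it does not work. Protocol 6.1.2 requires stable therapy for at least 30 days before screening, so a first dose of background therapy precedes consent, and SAEs between consent and randomisation would count as emergent. Participants who cannot tolerate lipid-lowering therapy are eligible and may have no dose at all.

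Three other replies also have force. Protocol 12.5.2 does contain one rule that works without a dose. The comparative wording in Protocol 3.2 covers a mixed list, some of it with no control counterpart, and no between-arm safety test is planned. And listings include all data.

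A reader might go further and infer that neither document offers any usable date for controls, that control-arm safety data are lost, or that the main results are at risk. The documents do not support this. The treatment-period rule exists, although it conflicts with the first-dose rule. SAEs are collected and listed in every arm. Efficacy is analysed on the Full Analysis Set, and new lipid-lowering therapy in Group 1 would still appear there as a protocol deviation (SAP 2.3.1; Table 5-4, COMD01 and COMD02).

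**Conclusion.** On the written definitions, Group 1 is outside the Safety Set: 0 of 300 controls, and at most 600 of 900 participants overall. The planned SAE, death, special-interest and registry tables, and the Safety Set medication summaries, therefore have no control column. The SAP's treatment-emergent rule and its AE and medication date imputations have no start date for undosed participants, and Protocol 12.5.2 is inconsistent with itself.

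This rests on the protocol's own definition of study treatment and on dosing as scheduled. What is lost is a set of planned summaries, including changes the deviation items do not name, such as a dose change of the same lipid-lowering drug. No data are lost, and the primary and key secondary efficacy analyses are untouched. It should be fixed before database lock.

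**What to change.** 1. **Safety Set.** Define it as participants who received at least one inclisiran injection, analysed as inclisiran, plus all randomised Group 1 participants who received none, analysed as standard of care plus behavioural support. This keeps one safety population grouped by treatment received. Participants assigned to Groups 2 or 3 but never injected stay outside; report their number and list their events.
2. **Start date.** Extend the SAP 2.1.1 fallback to the treatment-emergent rule (2.7) and to the AE and medication date imputations (5.1.2, 5.1.3), and state which visit is the randomisation visit. For the between-arm SAE and death tables, use the randomisation date held in the IRT as the start in all three arms. Tables anchored on first dose can be kept for Groups 2 and 3.
3. **Medication summaries.** Run the summaries of lipid-lowering therapy use and change on the Full Analysis Set or the corrected Safety Set.

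Record these in SAP section 4 as departures from Protocol 12.1, 12.3 and 12.5.2. The cost is minor wording and programming; Protocol 11.2 shows that randomisation dates are already tracked. The downside is that some pre-injection events enter the inclisiran columns of the comparative tables. With randomisation at most 14 days before treatment (Protocol 8.2) and follow-up to 30 days after Day 270, that is at most about 14/(14 + 270 + 30) = 4.5% of the observation time. The ±14-day allowance on Day 1 in Table 8-1 could widen it.

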#### 2.2.1 Subgroup of interest

No subgroup analysis is planned.

# 2.3 Patient disposition, demographics and other baseline characteristics

#### 2.3.1 Patient disposition

The overall number of participants who entered, completed, and discontinued the study will be summarized and listed, including the reasons for discontinuation. Duration on study is defined as: date of last known visit on study – date of first dose of treatment/ randomization visit, if no study treatment has been received.

The duration on study will be summarized by treatment group. The screening disposition will be based on SCR. The FAS will be used for the summary and listing of patient disposition. The number of participants in the FAS will be summarized by treatment group. Number of participants with protocol deviations will be tabulated by category (e.g., selection criteria not met, subject not withdrawn as per protocol, treatment deviation, prohibited concomitant medication, other), deviation using FAS. Listing of participants with protocol deviation will be provided.

The number of participants included in each analysis set will be tabulated using RAN. Participants exclusion from analysis sets will be summarized for all patients with reasons for exclusion (i.e. including both protocol and non-protocol deviations) and corresponding listing will be provided.

#### 2.3.2 Demographics and other baseline characteristics

Demographic and other baseline data including age, race, gender, baseline characteristics such as body height, smoking history, Dietary advice status, Exercise status; baseline disease characteristics like LDL-C, baseline use of other lipid-lowering therapies (yes, no), statin intolerance history(yes, no), baseline diabetes status determined by the fasting glucose ( $\geq$  7.0 mmol/L) or random glucose ( $\geq$  11.1 mmol/L) or HbA1C ( $\geq$  6.5% or 48 mmol/mol) or medical history, baseline measurements will be summarized descriptively by treatment group for FAS. Listings will also be provided.

| Novartis | Confidential | Page 14 of 37           |
|----------|--------------|-------------------------|
| SAP      |              | Study No. CKJX839A1GB01 |

Categorical data will be presented as frequencies and percentages by treatment group. For continuous data, non-missing observations, mean, standard deviation, median, 1st and 3rd quartile, minimum, and maximum will be presented.

No inferential statistics will be provided for baseline comparability among the treatment groups.

In addition, the following categorizations of continuous variables will be done:

- Age groups  $< 65, \ge 65$  and  $< 75, \ge 75$
- LDL-C subcategories Category 1:  $\leq 2.6 \text{ mmol/L}$ , > 2.6 mmol/L; Category 2:  $\leq 2.1 \text{ mmol/L}$ ,  $> 2.1 \leq 2.6 \text{ mmol/L}$ ,  $> 2.6 \leq 3.3 \text{ mmol/L}$  and > 3.3 mmol/L
- •

•

